*Please note that only one community health center out of their 25 clinics is currently delivering 2VIDA! as a clinical program and all of their clinics are offering the vaccine on site (no mini-vaccination stations). For the purposes of this research, we will randomize 6 community health centers and their surrounding communities that are predominantly Latinx and AA to receive either 2VIDA! or the standard of care for vaccine delivery (i.e. no components of 2VIDA! will be deployed). In order to avoid contamination, the community health center where the 2VIDA! was developed (i.e., Chula Vista) and is currently being implemented as a clinical program will be excluded from this study. Additionally, SYH is currently offering the vaccine at their community health centers, however, there is low vaccine uptake, therefore we believe this study will help increase interest in the vaccine and address vaccine hesitancy by working with the community.

6. BACKGROUND AND SIGNIFICANCE (2-3 paragraphs maximum)

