Spanish that are written at the 8th grade level (the average reading level of adults in the United States) that peer-health educators will distribute to community members during their visits to the participating SYH community centers, door-to-door, local supermarkets (SYH has a partnership with Northgate Gonzales Market), and community-based organizations (CBO's) in the selected communities. These materials have general information on COVID-19 as well as educational information and resources regarding COVID-19 prevention, symptoms, testing, contact tracing, COVID-19 vaccine (how it works, technology used, administration [2-dose series and importance of vaccine completion], safety concerns, benefits, risks, dispelling common misconceptions and misinformation, potential side effects and what to do), and other topics identified based on community needs. This information will be updated monthly to ensure the most up to date information. The goal is to distribute approximately 20,000 educational and outreach materials across the three randomly selected communities.

- **COVID-19 Community Outreach & Health Promotion.** Peer-health educators will work with local CBO's and facilitate a combination of live broadcast sessions, pre-recorded webinars, social media posts, and other outreach activities in English and Spanish reaching community members with information on the above COVID-19 related topics as well as other identified needs such as what to do if a family member is infected and where you can get the COVID-19 vaccine. The goal of this research activity is to reach 10,000 viewers (per session) in the various social media platforms in the three randomly selected communities.
- **COVID-19 Individual Health Education & Linkages to Medical and Supportive Services.** For the purposes of this research, SYH will establish a COVID-19 Resource Center within the participating health centers in the three randomly selected communities (intervention sites only) providing individual COVID-19 related health education and linkages to medical and supportive services for patients and community members in need of additional education and support regarding COVID-19 disease and COVID-19 vaccine.

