10. RECRUITMENT

Six SYHealth community health centers across San Diego County have been selected based on their serving predominantly Latinx and AA client population and having the Zip codes with the highest number of COVID-19 cases in the County. These clinics are located in National City, Logan Heights, Lincoln Park, Valencia Park and San Ysidro. Each clinic will be randomly selected and randomized evenly to either the intervention or control conditions, using computer-generated randomization plans prepared using SAS statistical software under the direction of the lead study statistician. Clinic-level randomization was selected to minimize between-arm contamination of intervention and control conditions. Participants from both intervention (n=500) and control sites (n=500) will be recruited using reactive recruitment, including the use of community partner social media platforms, and flyers distributed in the SYH target health centers and high traffic, readily visible areas, where eligible participants are likely to see them (e.g., grocery stores, local CBO's, parks, barber shop, cafés, food banks, gyms, local restaurants). Flyers will include study information and contact information for study staff. Likewise, the project staff publicized the rapid vaccine effort (e.g., mini-vaccination stations) by posting flyers that noted locations, dates, and times of vaccine distribution, and through presentations about the project at community meetings. Project staffing, training, and support, including the selection of nurses and outreach staff (e.g., peer-health educators and research assistants) with complementary research skills and personal knowledge of the community will be key to the success of the project. Two bilingual Latinx (one male and one female) and two AA (one male and one female) outreach workers trained in research ethics and protocols, and familiar with this population will approach individuals who appear to be eligible (Latinx and AA adults ages 16 years or older) at the SYH community centers and mini-vaccination stations in the participating communities, confirm eligibility, and describe the study to those eligible. Research staff will update time logs and continuously update our sampling frame until recruitment is finalized. The reason for refusal or ineligibility will be recorded. Extensive efforts will be made to have an equal representation of Latinx and Black community members and at least 40% women.

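### Phase I outreach and recruitment in both arms use the same kinds of channel, so controls can be enrolled from the Phase I audience, and no exposure measure by arm is specified

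*Protocol*

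**What the plan says.** **Delivery (Protocol section 8, Phase I).** "Peer-health educators will work with local CBO's and facilitate a combination of live broadcast sessions, pre-recorded webinars, social media posts" are the outreach tools. The goal is stated with a geographic scope: "The goal of this research activity is to reach 10,000 viewers (per session) in the various social media platforms", in a sentence that ends by naming the three intervention communities. Printed materials are handed out at the clinics, door to door, and at "local supermarkets (SYH has a partnership with Northgate Gonzales Market), and community-based organizations (CBO's) in the selected communities".

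**Recruitment (Protocol section 10).** "Participants from both intervention (n=500) and control sites (n=500) will be recruited using reactive recruitment, including the use of community partner social media platforms". Flyers go up in the clinics and in busy public places ("e.g., grocery stores, local CBO's, parks, barber shop, cafés, food banks, gyms, local restaurants"), and outreach workers approach people at the centers and stations. The same section says that the mini-vaccination stations, which exist only in the intervention arm, were advertised by flyer and at community meetings. It states no limit by arm.

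**Control condition (note at the end of section 5, repeated in section 8).** Controls receive "the standard of care for vaccine delivery (i.e. no components of 2VIDA! will be deployed".

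**Safeguards.** Clinics rather than individuals are randomised, with contamination given as the reason (section 10). The clinic where 2VIDA! was developed is excluded (sections 5 and 8). Aim 2 promises quantitative tracking of threats such as contamination (section 5). Section 8 and the SAP list outreach and health communication among the baseline and follow-up measures to be used as covariates.

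**The concern.** Randomising clinics separates the arms only if the intervention stays with the clinic or its community. A public post or broadcast does not stop at a community boundary. A person who answers a recruitment notice on a partner's feed is more likely than an average resident to have seen other content on that feed. If the feed also carries Phase I education, recruitment can draw into the control arm people who have already had part of the intervention.

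The effect would be to shrink the difference between arms, most directly on knowledge (H.1) and hesitancy, and to a lesser degree on uptake. If exposure is not recorded by arm, a null or small result will be hard to interpret: the intervention may not work, or the controls may have received some of it.

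**Working it through.** **1. Channels side by side.**

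| Channel type | Phase I delivery (section 8) | Recruitment of both arms (section 10) |
|---|---|---|
| Social media | Broadcasts, webinars and posts, run with local community-based organisations | Partners' platforms |
| Community-based organisations | Materials handed out there | Flyers |
| Food shops | Materials at supermarkets | Flyers at grocery stores |

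All three types appear in both columns. The printed strand of Phase I is tied to physical places in the selected communities. The social media strand is tied to them only by the stated goal.

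**2. What stands between the columns.** The eligibility lists (section 8, mini-vaccination stations, and section 12) contain no question about earlier contact with 2VIDA! outreach. The residence criterion speaks of three intervention communities but then names five, undivided by arm. No text assigns pages, feeds or stores to one use or the other. San Ysidro Health runs the clinics in both arms and is described, just before section 19, as the largest community partner, guiding the outreach. Its own pages are a plausible candidate for both uses, but no account is named.

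**3. Timing.** Section 8 places the survey in Phase II, and the station signs reuse artwork from Phase I. Phase I therefore appears to begin before enrolment, so exposure can precede a control's baseline survey.

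**4. Measurement.** The survey domains lettered a to i (sections 5 and 8) name no exposure to 2VIDA! components. Asking which components people received is given as an example for the focus groups, which are two groups of 8 to 10. The outreach and health communication measure appears only as a covariate. If it is taken after exposure, adjusting for it could remove part of the intervention effect.

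**5. Size.** The plan states power .90 for an effect of .20 at alpha .05, after moderate attrition. It gives neither the attrition rate nor the sidedness. Treating .20 as a standardised mean difference, two-sided, individual-level:

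- n per arm = 2(1.960 + 1.282)² / .20², which rounds up to 526.
- With 500 per arm and no attrition: power = Φ(.20 × √(500/2) − 1.960) = Φ(1.202) = .885.
- With 10% or 20% attrition: .851 or .807.

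Other readings come close to .90, such as one-sided with 15% attrition (.898), or baseline adjustment with an assumed correlation of .5 and 20% attrition (.904). The stated figure can therefore be approached but not pinned down. None of these variants allows for clustering or contamination. I use .885 as the reference.

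Let a share c of controls be exposed, and let exposure carry a fraction f of the full effect. The expected difference is then .20 × (1 − f·c), and power is Φ(difference × 15.811 − 1.960).

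| c (assumed) | f = 1 (full effect) | f = 0.5 (assumed) |
|---|---|---|
| 0 | .20, power .885 | .20, power .885 |
| 10% | .18, power .812 | .19, power .852 |
| 30% | .14, power .600 | .17, power .767 |

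The documents give no value for c or f. The f = 1 column is an upper bound on dilution for a given c, because a post cannot deliver the Resource Center, the stations or the tracing of missed second doses. With only six clinics the absolute power values are optimistic; the table shows direction and rough scale only.

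**The case against.** The plan does not ignore contamination. It randomises clinics, excludes the development site, states the communities that Phase I is meant for, and promises to track contamination quantitatively. The Resource Center and the stations are confined to intervention sites. Recruitment also runs through the clinics themselves. All of this stands, and it limits the point in four ways.

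- A reader might infer that Phase I has no geographic limit. That is wrong: the viewer goal names the three communities. What is missing is a means of carrying that out on social media.
- A reader might infer that the same pages and stores serve both purposes. The documents show overlap of channel type, not of particular accounts or shops.
- A reader might infer from 10,000 viewers per session that the audience must spill into control areas. No community population is given, so the number supports no such conclusion.
- A reader might infer that exposure will not be measured at all and that a null result would be uninterpretable. The survey instrument is not in the documents, an outreach measure is mentioned, and satisfaction with 2VIDA! is a listed domain. The supported statement is narrower: no exposure item, report by arm or analysis rule is specified.

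These limits leave the gap open. A stated audience is not a mechanism, and a promise to track is not yet an instrument.

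**Conclusion.** The plan as written allows controls to be enrolled from the Phase I audience and does not specify how anyone would know. The bias would run towards no difference in knowledge, hesitancy and uptake. Its size is unknown: dilution from .20 to .18 or .14 assumes that 10% or 30% of controls receive the full effect, and the true loss for a given share is probably smaller. The conclusion rests on the text comparison, not on those figures. It assumes that at least some partner feeds carry both recruitment notices and Phase I content, or that Phase I posts reach control-area residents; nothing in the documents prevents either. The remedy is cheap and would make the Aim 2 commitment deliverable, so the change should be made.

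**What to change.** 1. **Measure exposure in both arms.** Add a short checklist to the baseline and follow-up surveys: saw 2VIDA! printed materials; saw a broadcast or post; used the Resource Center; used a mini-vaccination station. Report it by arm as the Aim 2 contamination measure. Use it descriptively or in a sensitivity analysis, bearing in mind that there are only six clinics. State in the SAP that neither this checklist nor outreach exposure at follow-up is adjusted for in the main comparison.
2. **Separate recruitment from content, identically in both arms.** Post recruitment notices on pages or feeds that carry no 2VIDA! education. Do not restrict channels for controls alone: participants are enrolled after clinics are randomised, so arm-specific recruitment would risk exchanging dilution for selection bias of unknown direction.
3. **Carry out the stated scope.** Where the platform allows, target Phase I posts and broadcasts by location to the intervention communities, and count reach there.

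The cost is a few more survey items at two time points, slightly narrower outreach, and possibly slower recruitment.

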4. ESTIMATED DURATION OF THE STUDY

5 years

5. SPECIFIC AIMS (2 paragraphs maximum)

As of January 2021, the World Health Organization (WHO) reports that 90 million cases of COVID-19 (SARS-CoV-2) have been confirmed and have resulted in more than 1.9 million deaths globally.¹ Currently, the United States (U.S.) is the country with the largest number of infections and deaths due to COVID-19, with a total of 26 million infections and 454,596 deaths.² Furthermore, early findings that have examined COVID-19 demographics show that racial and ethnic minorities in the U.S. are bearing a disproportionate number of COVID-19 cases and deaths. Recent data from the Centers for Disease Control and Prevention (CDC) indicate that COVID-19 hospitalization rates among African American (AA) and Latinx people were both 4.7 times the rate of non-Hispanic white people³. While there's no evidence that people of color (POC) have genetic or biological factors that make them more likely to be affected by COVID-19, they are more likely to have underlying health conditions, live in multi-generational homes and densely populated areas, limited access to healthcare, and be essential workers.⁴ All of these factors contribute to higher rates of infection and adverse COVID-19 outcomes. Although COVID-19 preventive behaviors such as mask wearing, and social distancing have been shown to be effective in curbing the spread of the virus, acceptance and uptake of COVID-19 vaccines will be instrumental to ending the pandemic. However, public confidence in vaccination is fragile, especially among racial and ethnic minorities, likely due to historical racism in health care and human rights violations in research.⁵ COVID-19 vaccination programs will only succeed if there is widespread belief that available vaccines are safe and effective and that policies for prioritizing their distribution are equitable and evidence-based. To this end we have formed an intervention working group comprised of representatives from community and academic organizations including San Ysidro Health and UC San Diego, to address challenges in COVID-19 vaccination among Latinx and African American (AA) communities in Southern California. We have developed *2VIDA! (SARS-CoV-2 Vaccine Intervention Delivery for Adults in Southern California)* a multilevel intervention to address individual, social, and contextual factors related to access, acceptance, and uptake of the COVID-19 vaccine among Latinx and AA adults in San Diego. *2VIDA!* builds on our previous community-based participatory research (CBPR) efforts and was developed as a pilot clinical program in one of SYH community health centers. Through this proposal we seek to evaluate this program and its effects in increasing access, acceptance and uptake of the COVID-19 vaccine by scaling-up across 3 communities in South San Diego. *2VIDA!* centers on conducting COVID-19 Individual awareness and education, COVID-19 linkages to medical and supportive services, and COVID-19 Community Outreach and Health Promotion in the intervention sites (Phase 1); and offering the COVID-19 vaccine to Latinx and AA adults (≥ 16 years old) in SYH community health centers (CHC) and

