PHASE II. To evaluate the preliminary impact of 2VIDA! compared to the standard-of-care for COVID-19 vaccination services among Latinx and AA adults >16 years (N=1000) in San Diego. During Phase 2 we will offer the COVID-19 vaccine at the participating SYH community health centers and mini-vaccination stations that will be set-up in these communities (only intervention sites) as part of the intervention efforts (i.e., research activities) to increase access and uptake of the COVID-19 vaccine. We have identified various open spaces (e.g., public parks) in these communities to set-up the vaccination stations. SYH is currently offering the vaccine in their facilities as part of their standard of care. It is available to everyone who is eligible according to the state guidelines and does not depend on participating in this study. However, as part of 2VIDA! we will add these mini-vaccination stations to increase access to the vaccine (e.g., open after 5:00pm and on the weekends). Furthermore, data will be collected to assess individual, social, and contextual factors related to access, acceptance, and uptake of the COVID-19 vaccine including: a) sociodemographic characteristics; b) characteristics associated with social marginalization (e.g., homelessness, food insecurity); c) access to and utilization of health care; d) vaccination history, interest, hesitancy and uptake; e) perceptions of the COVID-19 vaccine (e.g., fears, myths, etc.); f) general health; and h) trust in government, research, and social agencies; i) satisfaction with 2VIDA! at baseline and 4-week follow-up. The survey will last approximately 20 minutes and will be self-administered in both English and Spanish. Following the survey participants will be offered the COVID-19 vaccine and the SYH staff will help them set-up an online appointment onsite for the 2nd dose (1 month follow-up) and will be asked to complete a 5 min survey during the follow-up visit. SYH has trained medical staff and a strict protocol for the storage, handling, and application of the vaccine. UCSD staff will not be involved in this process. Furthermore, participants will be asked to provide separate written consent in order to receive the vaccine that will be conducted by SYH staff. Additionally, two focus groups (FGs) will be conducted with members of Latinx and AA communities (n=8-10 participants per group) to obtain feedback on implementation and ways to improve future sustainability and scalability for future vaccination efforts among vulnerable underserved communities. FGs will be transcribed and reviewed for themes specific to 2VIDA! including personal and structural barriers to medical accurate information and the COVID-19 vaccine, benefits, challenges, feasibility, and scalability.

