
Mini-vaccination stations. We will set-up mini-vaccination stations in the parking of three public parks in the selected intervention sites to support the SYH community health centers. We will set-up signs with the *2VIDA!* project for participants to identify (e.g., same logo and illustrations used during Phase 1) and tent-lined lanes for eligible recipients to drive up. Research assistants will confirm eligibility with potential study participants via verbal assessment of the following inclusion criteria: 1) age 16 years or older; 2) identify as Latinx and/or AA; 3) biologically male or female; 4) be a resident of one of the three communities selected for the intervention (National City, Lincoln Park, Logan Heights, Valencia Park, San Ysidro); 5) literate in English or Spanish; 6) no known history of severe allergic reactions to any components of the vaccine; 7) no history of immune disease; 8) not be pregnant; 9) no plans to move from the area in the following 30 days; 10) able to provide voluntary informed consent; and 11) able to provide complete contact information for themselves (email and phone number) and two additional contact individuals for follow-up. Inside their car they will complete the 10-15 min. survey, receive the COVID-19 vaccine, and pull aside for a 15-minute observation period. We will also set-up additional tents with portable chairs at least 6 feet apart for participants who do not own a vehicle and want to receive the vaccine at the mini-stations. The stations will be opened Monday-Sunday from 7:00am-7:00pm based on the recommendations from our community partners (e.g., some individuals work early/late shifts). We will have two options for the vaccine – a one shot or a two-shot vaccine and the participants will select what type of vaccine they prefer. The vaccines will be available on a first come first-serve basis. For individuals who select a two-shot vaccine, the study staff will schedule the appointment for the participants on site when they receive the 1st dose of the vaccine (as they are waiting during observation period) and give them the date (confirmation). We will use the NextGen program to schedule the follow-up appointments for these participants. For participants who select a one-shot vaccine, they will be reminded that they will receive a text message and/or a link via email (based on their preference) to complete a follow-up survey in 4-weeks. Participants who select a two-shot vaccine will be asked to complete the follow-up survey (4-weeks) when they return for their second shot (during the observation period). We have noticed that percentage of our population has low digital literacy levels and/or limited access to internet or digital technologies which has made enrollment and follow-up challenging. In order to address these barriers, we are proposing to utilize Computer Assisted Telephone Interviewing (CATI)²⁰ and videoconferencing and screen sharing (VCSS).²¹ Both tools have been successfully used for many years in public health as well as by our community partner (SYH) on other similar federal-funded research projects. During enrollment, we would provide the participants with the option to complete the follow-up survey utilizing CATI or VCSS if they require assistance or have limited access to digital technologies. If they chose CATI or VCSS, following the completion of the follow-up survey we would send the incentive via a unique link similar to the follow-up for other participants. The entire team has been trained on these two platforms and would only be used for follow-up. Additionally, SYH will create a temporary patient ID for them and enter them in the system to schedule their second appointment. This is the software program that SYH is currently utilizing to follow-up for vaccine appointments. We believe that utilizing SYH existing infrastructure will allow sustainability and scalability of *2VIDA!*! The participants who select a two-shot vaccine will receive an email or automated

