access to COVID-19 vaccine, vaccine hesitancy). Additional measures at baseline and follow-up will be used as covariates (e.g., outreach and health communication, vaccine hesitancy or mistrust). Mean differences, both within and between treatment and control groups as well as group by treatment interaction effects will be analyzed. The targeted sample size is sufficient to detect a small effect size (.20) with power = .90 at alpha = .05 accounting for moderate participant attrition.

Descriptive Statistics. To describe the overall sample regarding demographics, structural and individual barriers, and potential covariates of intervention effects at baseline, prevalence statistics and means and standard deviation will be provided for all baseline variables; Cronbach's alpha of .70 will be required to be considered reliable. **Baseline Analyses to Detect Differences Between Treatment Groups.** Chi-square analyses and paired t-tests will be used to detect differences in demographics, knowledge of COVID-19 vaccine, access to COVID-19 vaccine, acceptance of COVID-19 vaccine and series completion, COVID-19 resource-seeking behaviors and linkage into care between intervention and control groups. Demographic variables included in these analyses will be age, gender, race/ethnicity, education, household income, marital status, and having insurance. Those variables differing across treatment groups at the $p < .20$ level will be included in subsequent adjusted outcome analyses. For the qualitative data analysis, final translated electronic transcripts will be imported into Dedoose. Analysis will be done through identification of recurrent themes following Crabtree and Miller's 5 step "interpretive process."¹⁹ First, transcripts will be read to identify common themes, codes will be developed and ~10% of data will be double coded and inter-rate reliability assessed. Coded text will be extracted and organized and read to identify emergent themes.⁶⁵ Matrices will be created to compare codes by themes (e.g., medical mistrust, discrimination, stigma, transportation, access to vaccination site, lack of insurance). Data will be utilized to refine *2VIDA!*, assess acceptability, and inform future vaccination efforts among underserved communities.

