Cover Page for ClinicalTrials.gov

Document: Statistical Analysis Plan

Official Study Title: Project 2VIDA! COVID-19 Vaccine Intervention Delivery for Adults in Southern California

NCT number: NCT05022472

Document date: February 5, 2021

STATISTICAL DESIGN AND POWER CALCULATIONS

We will approach overall data analyses using a multivariate repeated measures design (i.e., doubly multivariate) to assess mean differences in treatment and control groups on our primary (acceptance of COVID-19 vaccine and vaccine series completion) and secondary outcome variables (increased knowledge of COVID-19 vaccine, increased access to COVID-19 vaccine, vaccine hesitancy). Additional measures at baseline and follow-up will be used as covariates (e.g., outreach and health communication, vaccine hesitancy or mistrust). Mean differences, both within and between treatment and control groups as well as group by treatment interaction effects will be analyzed. The targeted sample size is sufficient to detect a small effect size (.20) with power = .90 at alpha = .05 accounting for moderate participant attrition. Descriptive Statistics. To describe the overall sample regarding demographics, structural and individual barriers, and potential covariates of intervention effects at baseline, prevalence statistics and means and standard deviation will be provided for all baseline variables; Cronbach's alpha of .70 will be required to be considered reliable. Baseline Analyses to Detect Differences Between Treatment Groups. Chi-square analyses and paired t-tests will be used to detect differences in demographics, knowledge of COVID-19 vaccine, access to COVID-19 vaccine, acceptance of COVID-19 vaccine and series completion, COVID-19 resource-seeking behaviors and linkage into care between intervention and control groups. Demographic variables included in these analyses will be age, gender, race/ethnicity, household income, marital status, and having insurance. Those variables differing across treatment groups at the $p < .20$ level will be included in subsequent adjusted outcome analyses.

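### The only baseline survey is taken at the Phase II vaccine visit, so change-from-baseline contrasts drop, and some planned covariates dilute, any Phase I effect that came before enrolment; the plan does not say which contrast decides

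*Protocol*

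**What the plan says.** **Phases.** Protocol Section 5 describes education, linkage and outreach "in the intervention sites (Phase 1); and offering the COVID-19 vaccine to Latinx and AA adults" at clinics and mini-stations as Phase 2. Section 8 says what Phase I covers: vaccine safety, benefits, risks, misconceptions and where to be vaccinated. The note to Section 5 says control sites receive no part of 2VIDA!.

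**Survey timing.** Data collection is described under Phase II in Section 8: "Following the survey participants will be offered the COVID-19 vaccine". At the mini-stations the survey is completed in the car just before the first dose. Station signs carry the "same logo and illustrations used during Phase 1", and satisfaction with 2VIDA! is among the items listed for baseline as well as 4 weeks.

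**Analysis.** Section 8 and the SAP plan a doubly multivariate repeated-measures analysis with within-group, between-group and interaction contrasts. Knowledge, access and hesitancy are secondary outcomes. Measures from baseline and from follow-up serve as covariates; the examples given are outreach and health communication, and hesitancy or mistrust. The SAP adds: "Chi-square analyses and paired t-tests will be used to detect differences in demographics, knowledge of COVID-19 vaccine, access to COVID-19 vaccine", and also in acceptance, series completion, resource-seeking and linkage. A sentence listing demographic variables follows. The next sentence sends the variables that differ at p < .20 into the adjusted outcome models.

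**Hypotheses.** Aim 1 words H.1 to H.3 as comparisons with control participants at follow-up.

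**The concern.** A baseline should precede the intervention. Here the education half of the programme may have reached intervention participants before their first survey, while controls have had none of it. Any difference between arms in knowledge, access or hesitancy at enrolment may then be partly an early result of the programme.

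A contrast that subtracts the enrolment score treats that early result as a starting difference and discards it. Covariates such as outreach exposure, hesitancy and anything measured at follow-up lie on the path from intervention to outcome, so adjusting for them absorbs part of the effect under study.

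What is at stake is chiefly H.1 and the access and hesitancy outcomes: a programme that works through early outreach could be reported as having little effect on them.

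**Working it through.** **The plan's own figure.** The SAP calls the sample "sufficient to detect a small effect size (.20) with power = .90 at alpha = .05", "accounting for moderate participant attrition". Read .20 as a standardised mean difference, two-sided, with 500 per arm and independent participants:

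- .20 / sqrt(2/500) = 3.162; 3.162 − 1.960 = 1.202; power = Φ(1.202) = .885.

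This is close to .90, but only with no attrition and no clustering. With 450 per arm (10% attrition) it is .851, and with 400 (20%) .807. The plan gives no attrition rate.

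No further power figures are derived on this basis, because Section 10 randomises six clinics, three per arm. With 500/3 ≈ 167 participants per clinic, the standard error of an arm difference is sqrt[(2/3)(ICC + (1 − ICC)/167)]. That is .103 at ICC .01 and .193 at ICC .05 (both ICCs assumed). A clinic-level t-test on 4 degrees of freedom then has power of about .32 and .13 for an effect of .20. The size of this point is therefore better given as what each contrast estimates, which does not depend on clustering.

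**What each contrast estimates.** Inputs: total effect at follow-up Δ = .20 SD (the plan's figure); s = share of Δ already present at enrolment in the intervention arm (assumed); rho = baseline/follow-up correlation (assumed .3 to .7). There is no other difference between arms at enrolment.

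- Follow-up between-arm difference: Δ
- Change score or group-by-time: Δ − sΔ = Δ(1 − s)
- Adjusted for the enrolment score (ANCOVA): Δ − rho·sΔ = Δ(1 − rho·s)

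| s | Follow-up | Change | ANCOVA, rho .3 | rho .5 | rho .7 |
|---|---|---|---|---|---|
| 0 | .20 | .20 | .20 | .20 | .20 |
| .25 | .20 | .15 | .185 | .175 | .165 |
| .5 | .20 | .10 | .17 | .15 | .13 |
| .75 | .20 | .05 | .155 | .125 | .095 |
| 1 | .20 | .00 | .14 | .10 | .06 |

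Simulation (4,000 runs, 500 per arm, rho = .5) agrees. At s = .5 the three estimates average .200, .101 and .151; at s = 1 they average .199, −.001 and .099.

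A change contrast thus loses all of the pre-enrolment effect, whatever rho is. Adjustment for the enrolment score loses the fraction rho of it. Adjusting for follow-up hesitancy or mistrust could remove more, but the documents give nothing from which to size that.

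**Which variables are adjusted for.** The covariate sentence names outreach exposure and hesitancy outright. Whether knowledge, access, acceptance, resource-seeking and linkage can also enter depends on how far back the p < .20 sentence refers: to the whole tested list, or only to the demographic variables named immediately before it.

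**The case against.** The strongest reply is that the between-arm comparison is already there. Aim 1 words its hypotheses that way and the SAP lists between-group differences. A reader might infer that the SAP rests H.1 on change from baseline; neither document says so. This stands. What remains is that several contrasts are planned, they answer different questions, and none is named as deciding.

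Other stronger readings also fail:

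- *All baseline adjustment removes the Phase I effect.* It removes only the fraction rho of the part that came before enrolment.
- *The p < .20 rule certainly pulls in knowledge and access.* The wording permits a demographics-only reading. The covariate sentence is a problem under either reading.
- *Intervention participants were certainly exposed before enrolment.* The order is inferred from the phase labels, the station signs and the baseline satisfaction item. Materials are updated monthly and handed out at clinic visits, so some exposure may coincide with or follow enrolment. Figure 1, which is not available here, may show the sequence.
- *Power falls from .885 to a stated lower value.* The .885 treats participants as independent and does not describe a trial of six clinics.
- *The enrolment difference measures the Phase I effect.* Recruitment follows clinic randomisation and takes place partly at stations that exist only in the intervention arm. With three clinics per arm, the standard deviation of a chance enrolment difference is about .10 at ICC .01 and .19 at ICC .05, as large as a plausible early effect. Selection also makes the direction of the net bias uncertain.

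Vaccine receipt and series completion follow the survey and are not differenced away, though the named covariates could absorb part of the effect on them.

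**Conclusion.** The point holds as a gap in specification with a real route to bias. No pre-Phase I measurement is described. For knowledge, access and hesitancy, change and group-by-time contrasts discard any effect that came before enrolment, and adjustment for the enrolment score discards about rho of it. The follow-up between-arm contrast keeps the effect, but the plan does not make it decisive. Outreach exposure, hesitancy or mistrust, and follow-up measures are unsuitable covariates because the intervention is meant to change them.

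The size is illustrative. With half of a .20 SD effect present at enrolment and rho = .5, the estimates are .10 (change) and .15 (ANCOVA) against .20. The share s and rho are assumptions, and s could be small. The comparison also assumes no clinic imbalance or selection at enrolment. The documents do not support saying that H.1 will be missed.

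**What to change.** In Protocol Section 8 (Data Analysis) and the SAP:

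1. Name the between-arm difference at the 4-week follow-up as the deciding contrast for knowledge, access and hesitancy, matching Aim 1, and analyse it with clinic as the randomised unit.
2. Limit the p < .20 rule explicitly to the listed demographic variables (the protocol's list includes education and the SAP's does not; align them). Delete outreach and health communication, hesitancy or mistrust, and all follow-up measures as covariates for every outcome contrast, including the primary ones.
3. Report the enrolment-score-adjusted and change analyses as labelled sensitivity analyses.
4. Report the enrolment difference descriptively, as a possible mix of early Phase I effect, clinic imbalance and selection, not as a Phase I effect.

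The change is to wording only. It gives up some precision and, with only six clinics, some control of differences that existed before the trial. The sensitivity analyses in item 3 would show how much the result depends on that choice.
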